Study Rationale	
Impaired balance in activation between left and right prefrontal cortex has been described in patients with PMDD, consistent with its view as a network disorder. In particular, similar to major depressive disorder, the balance between alpha oscillation power in the left and the right hemisphere is shifted towards the left in patients with PMDD, more so during the luteal phase. We hypothesize that normalization of alpha oscillations in women with PMDD may be accomplished with brain stimulation by application of weak electric currents through transcranial alternating current stimulation (tACS), thereby altering the temporal activity structure of electric signaling in the brain. In this study, we will obtain electroencephalograms (EEGs) to assess whether a single session of tACS will enhance bilateral alpha synchronization (8-12 Hz) (by reducing left prefrontal alpha power) and whether this varies by menstrual cycle phase. An exploratory objective will be to examine the severity of the PMDD symptoms collected daily during the stimulation cycle compared with the baseline cycle.

Study Objective(s)	
Primary
 
 To determine whether a single session of tACS will reduce left prefrontal alpha power and thereby restore alpha symmetry 
Secondary
 
 To determine whether the impact of tACS on alpha power and distribution differs across menstrual cycle phases
Test Article(s) (If Applicable)	
XCSITE 100 Stimulator
 
The device consists of the following main components/subsystems: 1. Tablet with user interface application (App) 2. Microprocessor 3. Function generator chip 4. Voltage controlled current source 5. Safety circuitry
 
First, the stimulation parameters are specified by the user through the app. The parameters are: 1. tDCS/tACS 2. Number of channels 3. Amplitude 4. Test duration 5. Frequency (for tACS) 6. Password. Next, the parameters are sent via Bluetooth to the microprocessor. The microprocessor interprets these parameters, and programs the function generator chip accordingly through a SPI. The function generator then creates the programmed waveform, which is ultimately a voltage signal. The voltage signal is applied to a voltage controlled current source, which generates the specified amount of current through an arbitrary load resistance.

Study Design	Repeated measure, open-label trial
Subject Population	
Inclusion Criteria:
 
 Age 18-52

key criteria for Inclusion and Exclusion:	
 · Have a prospectively confirmed diagnosis of PMDD · Regularly menstruating without hormonal contraceptives · Medication free or regularly taking medication that has no effect on the nervous system · Not currently pregnant or planning to become pregnant 
Exclusion Criteria:
 
 · Brain surgery or brain implants, including cochlear implants or aneurysm clips · Neurologic disease (e.g. epilepsy or brain tumor) · Traumatic brain injury · Pregnant or nursing · An unstable medical illness (e.g. congestive heart failure or end-stage kidney disease) · History of severe or recurrent substance abuse within 2 years of study enrollment · History of suicidal behavior within 5 years of study enrollment · UNC Department of Psychiatry faculty, employee, or trainee
Number Of Subjects	20
Study Duration	
Each subject's participation is expected to last approximately one month. Two tACS with EEG recording sessions will occur, one during the follicular phase (5-9 days after menstruation) and one in the luteal, premenstrual phase (9-13 days after ovulation). Subjects will test their urine at home each morning for approximately one week to determine ovulation. Each tACS/EEG session will last up to 90 minutes.
 
The entire study is expected to last four and a half years

Study Phases Screening Study Treatment	
(1) Screening: Subjects with a diagnosis of PMDD confirmed by participation in a PMDD diagnostic study will be screened for eligibility in the tACS Study and review the informed consent forms. (2) Intervention: After consent is obtained, subjects will be asked to notify study personnel when they begin menstruating. If the subject is randomized to receive tACS in the follicular phase first, they will schedule a tACS session within 9 days of the onset of menses. If they are randomized to receive tACS in the luteal phase first, the subjects will then perform a home urine ovulation test every morning until they receive a positive result, at which point they will schedule their tACS session 9-13 days after the positive test result. Each stimulation session will last 40 minutes, plus the time it takes to place electrodes. EEG will be recorded before and after stimulation. At the end of the first session, subjects will be instructed to complete daily symptom rating scales for one completed menstrual cycle, or about 28-32 days. The second tACS session will be identical to the first, except it will occur in the opposite menstrual cycle phase as the first session.

Efficacy Evaluations	Primary efficacy measurement will be changes in left prefrontal alpha power or distribution (asymmetry) following tACS
Pharmacokinetic Evaluations	Not Applicable
Safety Evaluations	Primary measurements that will be used to assess safety:

-
- Subject semi-structured interview
 - Physical symptom items on the Daily Record of Severity of Problems (DRSP)
-

Statistical And Analytic Plan

We will use a t-test of pre-post changes to examine effects of tACS on left prefrontal alpha oscillations (primary outcome) and differences in effects as function of menstrual cycle phase (secondary outcome). There will be two levels of each of the two repeated within-subjects measures (pre vs post stimulation and follicular vs luteal phase). Order of administration will be assessed by considering order as a between- subjects variable.

DATA AND SAFETY MONITORING PLAN

Previous studies employing tACS, a non-invasive, non-pharmacologic procedure, have shown tACS to be safe and devoid of serious adverse effects. However, tACS does have some mild side effects, such as transient mild tingling, burning, or itching under the electrode sites. In our experience to date, subjects have reported either absent or mild side effects, and there was no difference between the groups with the exception of “flickering lights” (or phosphenes, $p = 0.014$) (Alexander et al., in preparation). Nonetheless, we will employ the following safety measures: subjects will be told that they can stop the stimulation at any time during the procedure and research personnel present during these sessions will also check in with the subject periodically during the stimulation to see whether they are comfortable.. Each subject will receive a semi-structured interview at the conclusion of the stimulation, and any side effects of greater than mild severity will be reported to the study PI. Possible side effects will be more formally evaluated with the daily rating forms, which will ask the subject to rate physical symptoms such as fatigue, headache, pain as well as any symptoms (which the subject can provide in text in the DRSP). The study coordinator will review the subjects’ daily rating forms daily. The PI will review adverse events and side effects in an aggregate format across all subjects enrolled on a quarterly basis. Substantial clinical worsening (compared with the baseline cycles) may result in a subject’s discontinuation from the study, at the discretion of the PI. Development of suicidal ideation more than just passive ideation (i.e., sometimes I feel like life is not worth living – not uncommon in women with PMDD in their symptomatic phase) for any reason or any unanticipated serious side effect will result in the subject’s discontinuation. Failure of the subject to experience symptom attenuation following the cessation of menses will result in the subject’s evaluation, discontinuation from the study, and recommendation of therapeutic intervention if required. The PI is responsible for the assessment and, where appropriate, the reporting of any adverse effects, and the PI can be reached 24/7. Finally, there is a theoretical likelihood that stimulation of neuronal circuits can lead to seizure. However, no studies have reported seizure as a side effect in recent trials of transcranial stimulation for depression or schizophrenia. To further minimize this very small, theoretical likelihood of a seizure, we screen and exclude patients with personal and family history of neurological conditions from the study.

1 BACKGROUND AND RATIONALE

Introduction

Premenstrual Dysphoric Disorder (PMDD) describes the cyclic appearance of affective symptoms and resultant impairment during the luteal phase of the menstrual cycle. The objective of the experiment is to determine if transcranial alternating current electrical stimulation (tACS) will alter prefrontal alpha oscillatory frequencies in women with PMDD, disruption of which has been implicated in other mood disorders. A secondary objective is to determine if menstrual cycle phase will influence the effects of tACS on alpha oscillations. Demonstration of 'target engagement' (alterations in left prefrontal alpha oscillatory frequencies with tACS) is a necessary first step before moving forward with subsequent research that would test whether tACS is a potential treatment for this disorder - promising research in other mood disorders suggests that it may be.

The cause of PMDD is unknown, the morbidity substantial, and the identified treatments limited in their effectiveness, since 40% of PMDD women are non-responders to SSRIs (Yonkers et al. 1997) and many additional women are intolerant of antidepressant induced side effects. PMDD is prevalent (6-8% of women of reproductive age), attended by substantial morbidity, and hence a significant public health problem. Indeed, by World Health Calculations, PMDD is associated with 4.5 million Disability Adjusted Life Years in the US alone (Halbreich et al. 2003). The rationale for testing whether tACS differentially alters target engagement in the follicular versus luteal phases of the menstrual cycle is described below.

Differential Effects on Cortical Activity: The rationale for testing whether tACS differentially alters target engagement in the follicular versus luteal phases of the menstrual cycle is as follows: 1) Role of Hormones: While there is little evidence for ovarian dysfunction in PMDD (Rubinow et al. 1988) a role for the reproductive hormones is clearly implicated, since our own work and that of others has shown that suppression of ovarian function results in a complete remission of symptoms in a majority of women with PMDD, while adding back gonadal hormones results in the return of symptoms in women with PMDD, with no symptoms seen in controls (Schmidt et al. 1998). Both estradiol and progesterone appear capable of precipitating mood destabilization in this paradigm. Recently completed studies from our group further demonstrate that continuous administration of hormones for longer than one-month results in a sustained symptom remission subsequent to the initial precipitated episode. Thus, dysphoric mood states in PMDD appear to be induced by normal changes in gonadal hormones rather than by exposure to elevated hormone levels (i.e., women with PMDD are differentially sensitive to the mood dysregulatory effects of reproductive steroids).

Although there is substantial literature demonstrating the effects of reproductive steroids and, by extension, the menstrual cycle on cortical activity, the usually described effects are disturbed in women with PMDD. Examples include the following: 1) in normal women, activation of the medial orbitofrontal cortex is diminished during the luteal phase and the affective valence of the stimulus to which it responds is reversed (i.e., it responds only to negative stimuli rather than to positive stimuli, as occurs during the follicular phase). These changes are absent in women with PMDD. (Protopopescu et al. 2008) 2) in normal women during the luteal phase, there is an increase in cortical inhibition - a

presumed effect of the GABA receptor activating effects of the progesterone metabolite allopregnanolone. This effect is absent in women with PMDD (Smith et al. 2003). Both animal and human data further suggest the role of a disturbed cortical response to progesterone-derived neurosteroids in PMDD (Epperson et al. 2002; Shen et al. 2007). Thus, sudden changes in the levels of allopregnanolone (as occurs at the start of the luteal phase with increasing levels of progesterone) result in subcortical excitability and irritability in rodents (Shen et al. 2007), while elimination of changes in progesterone-derived neurosteroids (with neurosteroid synthesis inhibition) successfully prevents the emergence of the dysphoric state in PMDD.

Differential Network Activation: Psychiatric disorders characterized by dysregulation of affective state –depression and PMDD - are increasingly recognized as are “network disorders” in which aberrant electric signaling in large-scale neuronal networks mediates the clinical symptoms. Recent studies have documented impaired balance in activation between left and right prefrontal cortex in patients with PMDD (Baehr, Rosenfeld et al. 2004; Accortt, Stewart et al. 2011; Lin, Tsai et al. 2013). In particular, similar to major depressive disorder (Henriques and Davidson 1990), the balance between alpha oscillation power in the left and the right hemisphere is shifted towards the left in patients with PMDD. The presence of alpha oscillations corresponds to a relative decrease in neuronal activity (inverse relationship). Therefore, such a left-shifted alpha asymmetry is indicative of hypoactivation of the left hemisphere – a common finding in imaging studies of patients with MDD (Grimm, Beck et al. 2008). Since this asymmetry is exacerbated during the luteal but not the follicular phase (corresponding to the time course of symptom presentation in PMDD, (Baehr, Rosenfeld et al. 2004; Lin, Tsai et al. 2013), we hypothesize that successful normalization of alpha oscillations in women with PMDD would be a plausible approach to symptom remediation. This network level intervention can be accomplished with brain stimulation by application of weak electric currents, a non-invasive approach to modulating intrinsic cortical network dynamics. The advantage of this approach is twofold: it is non-pharmacologic and thus avoids the otherwise attendant side effects; and it will provide systems level insights into the pathophysiology underlying mood state dysregulation.

Brain stimulation by constant electric currents applied to the scalp (tDCs) modulates neuronal excitability in humans (Wagner, Valero-Cabre et al. 2007; Zaghi, Acar et al. 2010; Stagg and Nitsche 2011). Transcranial current stimulation with sine-wave stimulation waveforms (transcranial alternating current stimulation, tACS) likely enhances cortical oscillations in a frequency specific manner. The mechanisms of weak electric fields generated by tDCS and tACS previously have been demonstrated to interact with cortical network activity by altering the temporal activity structure of electric signaling in cortex ([name] and McCormick 2010; Ali, Sellers et al. 2013). In this study, we will assess whether tACS will decrease left frontal alpha power (8-12 Hz) and whether the extent of the decrease varies by menstrual cycle phase. An exploratory objective will be to examine the severity of the PMDD symptoms collected daily during the stimulation cycle and compare that severity with baseline symptoms ratings collected during the PMDD diagnostic study from which these participants will be recruited. The rationale for this stimulation is the known deficits in the overall structure of cortical activity in this frequency band in patients with mood disorders (Henriques and Davidson 1990; Baehr, Rosenfeld et al. 2004; Bruder, Sedoruk et al. 2008; Accortt, Stewart et al.

2011; Lin, Tsai et al. 2013) and the previously demonstrate clinical benefits of tDCS in the treatment of mood disorders (Berlim, Van den Eynde et al. 2013; Brunoni, Valiengo et al. 2013). In this study, we will use more targeted stimulation waveforms by employing bilateral tACS instead of tDCS. We hypothesize that this choice of a more sophisticated waveform that directly enhances synchronization between the two hemispheres may be more effective in engaging the target. tDCS modulates overall activity levels of the targeted cortical area in a non-specific manner. Here, however, we propose to evaluate a more specific stimulation modality, tACS, (10 Hz stimulation frequency) that has been shown to selectively enhance cortical alpha rhythms (Neuling et al. 2013). Since the selected patient population reportedly exhibits specific deficits in the alpha frequency band, our stimulation approach will provide a more targeted and therefore possibly a more effective manipulation.

Protocol History: This protocol was originally designed to test the therapeutic efficacy of tACS in PMDD in a double blind, randomized, sham controlled, cross-over study of 5 tACS sessions. We were unable to recruit subjects, largely consequent to the many daily treatment sessions required. We subsequently changed the primary focus of the study to that of determining whether a single session of tACS engaged left prefrontal cortical alpha oscillations and, by reducing them, reduced alpha asymmetry. We further asked whether this effect was menstrual cycle phase-dependent. If target engagement was demonstrated, we then intended to perform a follow-up study to assess clinical efficacy, particularly but not exclusively if there were any evidence for reduction of mood symptoms on the exploratory analysis.

Name and Description of Investigational Product or Intervention

XCSITE100 Stimulator

We will be using the XCSITE100 stimulator designed in the [name] Lab for investigational purposes. The device is not implanted and has not been designed for or being used to support or sustain human life. This device does not have a potential for serious risk to the health, safety, or welfare of the participant. There has never been an instance of serious side-effect reported due to the use of transcranial brain stimulation. Previous studies in the [name] lab that used comparable devices (i.e., the commercial, CE-certified NeuroConn Plus stimulator) have always been classified as “non-significant risk” by the full UNC IRB. The NeuroConn Plus stimulator and the XCSITE100 stimulator are electrically equivalent and provide the same stimulation.

The XCSITE100 is the first non-invasive brain stimulator designed for research purposes to provide an active sham for tACS and record the stimulation output for later validation. This stimulator may apply either tDCS or tACS for up to 40 minutes (2400 seconds) with appropriate current ramp-up at the beginning of stimulation and ramp-down at the end of stimulation. Both tDCS and tACS may be applied for currents between 100 μ A and 2 mA (peak-to-peak for tACS).

The stimulator has two main components:

1. Android tablet with user interface application (i.e., App)
2. Stimulator with:
 - a. Microprocessor

- b. Function generator chip
- c. Voltage controlled current source
- d. Safety circuitry

To ensure appropriate blinding for each stimulation session, there are designated unblinded individuals to ensure the appropriate stimulation parameters are applied to each participant. These individuals will not interact with participants and will only be involved with the creation of a study file and validation of stimulation waveform.

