6 STATISTICAL CONSIDERATION

This is repeated, single intervention (tACS) administered during the follicular and luteal phase. Change in left prefrontal alpha power on EEG is the primary outcomes. Effect of menstrual cycle phase is the secondary outcome. We plan to analyze our data using a repeated measure analysis of variance (ANOVA-R), with two within subject variables, each with two levels: time (pre vs post tACS), and menstrual cycle phase (follicular vs luteal). We will assess any effects of order of administration (follicular first vs luteal first) by including order as a between-subjects variable.

Clinical symptoms will be quantified as the mean of daily nighttime ratings (individual symptoms rated from 1 to 6) collected in the follicular (days 4 – 9) and luteal phases (the 6 days preceding menses) as recorded in the DRSP.

Decrease in left prefrontal power (reflection of reduction in alpha asymmetry) will be calculated by comparing results from the following time points: 1) immediately before the stimulation and 2) immediately following the stimulation in each of the follicular and luteal phases.

The main intent of this study is to conduct a pilot study, the results of which could be used in a larger trial that is appropriately powered for efficacy. Nonetheless, we intend to determine whether tACS influences alpha coherence on EEG. Due to the novelty of the application and the treatment strategy, we do not have all the required parameters to estimate the power for the repeated measure design on alpha coherence on EEG. However, the primary purpose is to demonstrate tACS associated changes in alpha coherence and whether that differs by cycle phase. The aim to demonstrate ‘target engagement’ does not necessarily lend itself to traditional power calculations and we will rely on [name] extensive experience with analyzing these data. In his experience, he is confident that if, in fact, if there are menstrual cycle differences in alpha coherence, 20 participants will be sufficient to demonstrate that effect.

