6.3 Statistical Methods

Baseline Data: alpha oscillations in left frontal cortex before stimulation; severity of luteal phase symptoms in screening DRSP.

Efficacy Analysis: This is repeated, single intervention (tACS) administered during the follicular and luteal phase. Change in left prefrontal alpha power on EEG is the primary outcome. Effect of menstrual cycle phase is the secondary outcome. We will use a t-test of pre-post changes to examine effects of tACS on left prefrontal alpha oscillations (primary outcome) and differences in effects as function of menstrual cycle phase (secondary outcome). There will be two levels of each of the two repeated within-subjects measures (pre vs post stimulation and follicular vs luteal phase). Order of administration will be assessed by considering order as a between- subjects variable.

Exploratory analysis: Assessment of possible changes in mood will be assessed with linear mixed model regression analysis comparing mean luteal phase core affective symptoms (depression, irritability) after stimulation with means during baseline.

Pharmacokinetic Analysis (if applicable): not applicable

Safety Analysis - The PI will review any adverse effects and will quarterly review aggregated data, which will be recorded descriptively. Safety/ Tolerability will be assessed in two ways: 1) with somatic symptoms contained within the DRSP, completed daily, and with symptoms reviewed daily by the research coordinator. Any symptoms of moderate or greater severity appearing proximate to the tACS session will be reported to the PI. 2) with a semi-structured interview at the end of each tACS session, inquiring about possible side effects during the procedure (e.g., tingling, flickering lights, itching, burning sensation, headache, neck pain, scalp pain). Side effects of moderate or greater severity will be reported to the PI, who will also review aggregate data at the end of the experiment.

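### The plan reads a fall in left prefrontal alpha as restored symmetry without specifying a check that alpha is left-shifted before stimulation or falls relative to the right

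*Combined protocol and SAP*

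**What the plan says.** **The inference.** The synopsis states the primary objective as "To determine whether a single session of tACS will reduce left prefrontal alpha power and thereby restore alpha symmetry". Section 6 (Statistical Consideration) builds the same step into the outcome: "Decrease in left prefrontal power (reflection of reduction in alpha asymmetry) will be calculated by comparing results". Section 2 and the Protocol History in section 1 make the same link.

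**The premise.** Section 1 (Differential Network Activation) cites earlier studies for the statement that "the balance between alpha oscillation power in the left and the right hemisphere is shifted towards the left in patients with PMDD". It then gives the phase pattern: "Since this asymmetry is exacerbated during the luteal but not the follicular phase". The synopsis words this differently: alpha balance "is shifted towards the left in patients with PMDD, more so during the luteal phase". No mean, SD or proportion of women with a left shift is given.

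**What is required or measured.** Sections 3.4 and 4.1 base entry on a symptom-rated PMDD diagnosis plus general criteria, none of them concerning EEG. Section 5 lists left prefrontal alpha as the baseline EEG measure, and the only EEG item under Baseline Data in section 6.3 is "alpha oscillations in left frontal cortex before stimulation". The primary endpoint in section 6.1 is also left-sided only. Objective 2.1.2 and the synopsis efficacy measure do name symmetry or asymmetry, but section 6 gives no left-right index, direction, baseline summary or analysis for it.

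**The concern.** To restore symmetry is to move from an asymmetric state toward a symmetric one. A fall on the left shows this only if two things hold: left alpha was higher than right beforehand, and left fell more than right. The plan assumes the first from the literature and does not specify a check of the second, although stimulation is applied over both F3 and F4 and right-sided alpha may change too.

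A significant fall in left alpha could therefore be reported as restored symmetry when the recordings show no such thing, or show the reverse. What is at stake is the truth of the symmetry statement in the study's stated objective. The left-power result itself is not in question.

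**Working it through.** The plan gives no figure for asymmetry, so there is nothing of its own to reproduce here. The check is algebra plus illustrations whose inputs are assumed.

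**Index.** Let A = ln(left alpha) − ln(right alpha). A > 0 is a left shift and A = 0 is symmetry.

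**One woman, right side unchanged.** If left alpha falls by f on the log scale, A becomes A − f. She ends further from symmetry when |A − f| > |A|, that is, when A < f/2. This covers women who start symmetric or right-shifted, and also those with a small left shift who overshoot.

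Take an assumed 15% left fall, so f = −ln(0.85) = 0.163 and f/2 = 0.081:

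| Left/right before | A before | A after | Direction |
|---|---|---|---|
| 1.20 | +0.18 | +0.02 | toward symmetry |
| 1.00 | 0.00 | −0.16 | away |
| 0.90 | −0.11 | −0.27 | away |

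The proportional fall in left alpha is the same in all three rows, so a left-only endpoint cannot tell them apart.

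**Both sides fall.** If right alpha falls by the same proportion, A does not change. Section 6 would still read the left fall as reduced asymmetry.

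**How many women?** Suppose baseline A is normal with mean m and SD s, every woman has the same left fall f, and the right side is unchanged. The share moved away from symmetry is Φ((f/2 − m)/s). In units of s:

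| Mean left shift m | f = 0.2 | f = 0.5 | f = 1.0 |
|---|---|---|---|
| 0 | 54% | 60% | 69% |
| 0.5 | 34% | 40% | 50% |
| 1.0 | 18% | 23% | 31% |
| 1.5 | 8% | 11% | 16% |

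The answer runs from 8% to 69% depending on m and f, and the documents supply neither. The table shows that the number is unknown; no cell in it is an estimate for this trial.

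**Would absolute asymmetry be a good main measure?** Under the same normal model, mean |A| = s√(2/π)·exp(−m²/2s²) + m[1 − 2Φ(−m/s)]. With s = 1:
- m = 0.5: 0.798 × 0.882 + 0.5 × 0.383 = 0.896
- m = 0: 0.798

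Removing a mean left shift of 0.5 SD completely, with the spread unchanged, lowers mean |A| by only about 0.10 SD, while the signed mean moves by the full 0.5 SD. With 20 women, absolute asymmetry is too blunt to carry the test. Signed change read against the baseline value is the better choice.

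**The case against.** **The trial's decision rests on left alpha, not on symmetry.** The Introduction in section 1 defines target engagement as altered left prefrontal alpha, and the Protocol History makes the follow-up study conditional on target engagement. Objective 2.1.1, section 5.1 and the endpoint agree. This stands. A reader might infer that a false symmetry finding would by itself trigger the next study; the documents do not support that.

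**Phase is already separated.** Section 6 makes phase a within-subject factor and takes the pre-post comparison in each phase, and section 6.2 makes the phase difference the secondary endpoint. This also stands. A reader might infer that pooling the phases hides a luteal effect, but the plan provides the comparison that would show it. That comparison concerns change in left alpha, however, and does not show whether either phase began left-shifted.

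**Not exacerbated is not absent.** A reader might take section 1 to mean that follicular alpha is symmetric. It does not say so, and the synopsis wording implies some shift outside the luteal phase. The follicular starting point is simply unknown.

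**Asymmetry is already an objective, and EEG precedes each session.** This is partly right. If usable right frontal channels are recorded, baseline asymmetry can be computed, so the gap is in the specified analysis and not necessarily in the data. But naming a change in symmetry, with no index and no baseline value, does not show whether symmetry was approached.

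**Conclusion.** The point holds as a gap in specification and interpretation. The plan equates a left-sided fall with restored symmetry or reduced asymmetry. That is valid only when alpha starts left-shifted and left falls relative to right, and the plan specifies a check of neither. Where alpha is not left-shifted beforehand, a selective left fall increases asymmetry and would still be read as success.

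The size cannot be stated. A reader might want a count out of the 20 women, but any count would rest on an assumed mean and SD of asymmetry, an assumed size of fall and an unchanged right side. The conclusion itself needs only the definition of symmetry and the plan's own wording.

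The left-power analysis and the sample size are unaffected. The change is worth making because the stated objective includes the symmetry claim and the correction is cheap.

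**What to change.** Leave eligibility and the left-power endpoint as they are. Selecting women on measured asymmetry would bring in regression to the mean. Use the EEG already recorded before and after each session.

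1. In section 6.3, Baseline Data, add pre-stimulation left-right log alpha asymmetry by phase, with its mean and confidence interval. Name the homologous left and right frontal EEG channels. F3 and F4 are given only as stimulation sites and the recording montage is not listed, so confirm that usable right frontal channels exist.
2. For objective 2.1.2, analyse the signed pre-post change in this index by phase, read against its baseline value. Show change in absolute asymmetry as a descriptive supplement only.
3. Delete the parenthesis in section 6 that equates a left fall with reduced asymmetry. Use the term restored symmetry only for a phase whose baseline confidence interval shows a left shift and whose mean asymmetry moves toward zero. Otherwise report changed left alpha power. Align the synopsis objective with this rule.

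The cost is one derived variable and some wording, with no new visits or women. The downside is that a symmetry claim becomes harder to make: with 20 women, the baseline interval may not exclude zero even if a modest left shift is present. The rule also concerns the phase mean, so it supports a statement about the group and not about each woman.
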